5.10.4 CEC

A CEC will be responsible for providing an independent review and adjudication of the following data:

- Events that could contribute to primary endpoints for either trial arm, to determine which events meet primary endpoint qualification, including:
 - All cardiovascular hospitalizations, cardiovascular emergency department visits, and cardiovascular hospital outpatient visits, all defined as a hospital visit with the primary cause being cardiovascular in nature, as reported by the Investigator
 - All deaths
 - Any hospitalizations which, when reviewed by the Sponsor, could potentially meet endpoint qualification
- HFHs that occurred within 12 months prior to baseline
- All events that could contribute to the secondary safety endpoint for either trial arm including ADEs, SADEs, and UADEs

All attempts will be made to blind the CEC to the treatment group assignment. The function, responsibilities and membership of the CEC will be described in greater detail in a CEC charter.

6 Statistical Considerations

The following section describes the statistical methods for the clinical trial and justification of the design. Additional details on statistical analyses, including sensitivity analyses, poolability analyses, subgroup analyses and analysis of descriptive endpoint(s) will be described in a separate Statistical Analysis Plan (SAP). Hypothesis tests will be 1-sided and conducted at a significance level of 2.5% unless stated otherwise.

6.1 GUIDE-HF Randomized Arm

6.1.1 Primary Endpoint

The primary endpoint is a composite of recurrent HFHs or emergency department/hospital outpatient observation visits for intravenous diuretic therapy or all-cause mortality (referred to as Composite Endpoint) at 12 months post-implantation. [REDACTED]

[REDACTED] The analysis population will include subjects enrolled in the Randomized Arm, successfully implanted, and randomized to either Treatment or Control Groups.

To demonstrate effectiveness of PA pressure-guided HF management compared to standard-of-care-guided HF management, the following hypothesis will be tested:

H_0 : HR for the Composite Endpoint at 12 months (Treatment to Control) ≥ 1

H_1 : HR for the Composite Endpoint at 12 months (Treatment to Control) < 1

6.1.1.1 Analysis Methods

6.1.1.2 Sample Size

6.1.1.3 Criteria for Success

The primary endpoint must be met in order for the GUIDE-HF Randomized Arm to be considered successful. Primary and secondary endpoints will be used to support label claims.

6.1.1.4 Missing Data

6.1.2 Secondary Endpoints

The secondary effectiveness endpoints of the GUIDE-HF Randomized Arm include the composite of HFH and emergency department/hospital outpatient observation visits for intravenous diuretic therapy at 12 months post-implantation (i.e., HFH + HFH Equivalents) as well as health status, as assessed by the EQ-5D-5L Questionnaire and the KCCQ-12, and the 6MHW test at baseline, 6, and 12 months post-implantation. In addition, the individual components of the primary endpoint will each be evaluated as descriptive secondary effectiveness endpoints: HFH at 12 months post-implantation, emergency department/hospital outpatient observation visits for intravenous diuretic therapy at 12 months post-implantation, and all-cause mortality at 12 months post-implantation. [REDACTED]

[REDACTED] The analysis population for the secondary effectiveness endpoints will include subjects enrolled in the Randomized Arm, successfully implanted, and randomized to either Treatment or Control Groups.

The secondary safety endpoint of the GUIDE-HF Randomized Arm is freedom from DSRCs at 12 months post-implantation. The analysis population for the secondary safety endpoint will include subjects enrolled in the Randomized Arm (i.e. with an attempted implant, whether successful or unsuccessful).

6.1.2.1 HFH + HFH Equivalents at 12 Months Post-Implantation

To demonstrate effectiveness of PAP-guided HF management compared to standard-of-care-guided HF management with respect to HFH + HFH Equivalents, the following hypothesis will be tested:

H_0 : HR for HFH + HFH Equivalents at 12 months (Treatment to Control) ≥ 1

H_1 : HR for HFH + HFH Equivalents at 12 months (Treatment to Control) < 1

6.1.2.1.1 Analysis Methods

6.1.2.2 EQ-5D-5L at 6 and 12 Months Post-Implantation

To demonstrate effectiveness of PA pressure-guided HF management compared to standard-of-care-guided HF management with respect to the EQ-5D-5L, the following hypothesis will be tested for the EQ-5D-5L visual analogue scale (VAS):

H_0 : Treatment effect_{EQ-5D-5L VAS} ≤ 0

H_1 : Treatment effect_{EQ-5D-5L VAS} > 0

6.1.2.2.1 Analysis Methods

he null hypothesis will be rejected if the [REDACTED] show benefit of Treatment over Control and the p-value is less than 2.5% using a one-sided test.

6.1.2.3 KCCQ-12 at 6 and 12 Months

To demonstrate effectiveness of PA pressure-guided HF management compared to standard-of-care-guided HF management with respect to the KCCQ-12, the following hypothesis will be tested:

H_0 : Treatment effect_{KCCQ-12 Overall Summary Score} ≤ 0

H_1 : Treatment effect_{KCCQ-12 Overall Summary Score} > 0

6.1.2.3.1 Analysis Methods

The hypothesis will be evaluated using a mixed linear model with repeated measures. Treatment

The null hypothesis will be rejected if the [REDACTED] show benefit of Treatment over Control and the p-value is less than 2.5% using a one-sided test.

6.1.2.4 6MHW Test at 6 and 12 Months Post-Implantation

To demonstrate effectiveness of PA pressure-guided HF management compared to standard-of-care-guided HF management with respect to the 6MHW test, the following hypothesis will be tested:

H_0 : Treatment effect_{6MHW} ≤ 0

H_1 : Treatment effect_{6MHW} > 0

6.1.2.4.1 Analysis Methods

[REDACTED]
[REDACTED]
[REDACTED] The
null hypothesis will be rejected if the [REDACTED] show benefit of Treatment over Control and the p-value is less than 2.5% using a one-sided test.

6.1.2.5 Individual Components of the Primary Endpoint

6.1.2.5.1 HFH at 12 months post-implantation

6.1.2.5.2 HFH Equivalents at 12 months post-implantation

6.1.2.5.3 All-Cause Mortality at 12 months post-Implantation

6.1.2.6 Secondary Safety Endpoint: Freedom from DSRCs over 12 Months Post-Implantation

6.2 GUIDE-HF Single Arm

6.2.1 Primary Endpoint

The primary endpoint is a composite of recurrent HFHs or emergency department/hospital outpatient observation visits for intravenous diuretic therapy or all-cause mortality at 12 months post-implantation (identical to the Randomized Arm primary endpoint). The two subject groups to be compared are a) subjects having elevated NT-proBNP (or BNP) but without having a HFH in the year prior (i.e., **elevated NT-proBNP (or BNP) only subjects**) and b) subjects having a HFH in the year prior but without elevated NT-proBNP (or BNP) (i.e., **prior HFH only subjects**). The analysis population of the GUIDE-HF Single Arm primary endpoint will include subjects enrolled into the Single Arm and successfully implanted with either **elevated NT-proBNP (or BNP) only** or **a prior HFH only**. Subjects with both elevated NT-proBNP (or BNP) and a prior HFH will not be included in the analysis for the primary endpoint.

To demonstrate equivalence of outcomes between subjects with elevated NT-proBNP (or BNP) only and those with prior HFH only, the following hypothesis will be tested:

H_{0a} : $\ln[\text{HR for Composite Endpoint (Elevated NT-proBNP (or BNP) Only vs. Prior HFH Only)}] \leq -0.2877$

H_{0b} : $\ln[\text{HR for Composite Endpoint (Elevated NT-proBNP (or BNP) Only vs. Prior HFH Only)}] \geq 0.2877$

H_1 : $-0.2877 < \ln[\text{HR for Composite Endpoint (Elevated NT-proBNP (or BNP) Only vs. Prior HFH Only)}] < 0.2877$

Where \ln is the natural log

6.2.1.1 Analysis Methods

The hypothesis will be tested at the 5% significance level. [REDACTED]

[REDACTED] The test will be successful and equivalence will be established only if both null hypotheses are rejected.

6.2.1.2 Sample Size

6.2.1.3 Criteria for Success

The primary endpoint must be met in order for the GUIDE-HF Single Arm to be considered successful. The primary and secondary endpoints will be used to support label claims.

6.2.2 Secondary Endpoints

The secondary effectiveness endpoints of the GUIDE-HF Single Arm include the composite of HFH and emergency department/hospital outpatient observation visits for intravenous diuretic therapy at 12 months post-implantation (i.e., HFH + HFH Equivalents) as well as the comparison of the annualized rate of recurrent HFHs at 12 months post-implantation to the annualized rate of recurrent HFHs in the 12 months prior to implantation. In addition, the individual components of the primary endpoint will each be evaluated as descriptive secondary effectiveness endpoints: HFH at 12 months post-implantation, emergency department/hospital outpatient observation visits for intravenous diuretic therapy at 12 months post-implantation, and all-cause mortality at 12 months post-implantation. [REDACTED]

The secondary safety endpoint of the GUIDE-HF Single Arm is freedom from DSRCs at 12 months post-implantation. The analysis population for the secondary safety endpoint will include subjects enrolled in the Single Arm (i.e. with an attempted implant, whether successful or unsuccessful).

6.2.2.1 HFH + HFH Equivalents at 12 Months Post-Implantation

To demonstrate equivalence of HFH + HFH Equivalents between elevated NT-proBNP (or BNP) only subjects and prior HFH only subjects, the following hypothesis will be tested for HFH + HFH Equivalents at 12 months:

$H_{0a}: \ln[\text{HR for HFH+HFH Equivalents (Elevated NT-proBNP Only vs. Prior HFH Only)}] \leq -0.2877$

$H_{0b}: \ln[\text{HR for HFH+HFH Equivalents (Elevated NT-proBNP Only vs. Prior HFH Only)}] \geq 0.2877$

$H_1: -0.2877 < \ln[\text{HR for HFH+HFH Equivalents (Elevated NT-proBNP Only vs. Prior HFH Only)}] < 0.2877$

Where \ln is the natural log

6.2.2.1.1 Analysis Methods

[REDACTED]

6.2.2.2 HFHs at 12 Months Post- vs. Pre-Implantation

To demonstrate effectiveness of PA pressure-guided HF management with respect to the goal of reducing HFHs, the following hypothesis will be tested:

H_0 : HR for annualized HFHs at 12 months (Rate at 1 year post-implant to Rate at 1 year pre-implant) ≥ 1
 H_1 : HR for annualized HFHs at 12 months (Rate at 1 year post-implant to Rate at 1 year pre-implant) < 1

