4.4.1 Inclusion Criteria

To participate in this clinical trial and receive a CardioMEMS™ HF System implant, subjects must meet all of the following inclusion criteria:

1. Diagnosis and treatment for HF (regardless of LVEF) for > 90 days prior to the date of consent:
 - a. Subjects should be on stable, optimally titrated medical therapy for at least 30 days, as recommended according to current AHA/American College of Cardiology (ACC) guidelines as standard-of-care for HF therapy in the United States, with any intolerance documented.
2. **GUIDE-HF Randomized Arm Only:** NYHA Class II, III or IV HF symptoms documented within 30 days prior to consent.
3. **GUIDE-HF Single Arm Only:** NYHA Class III HF symptoms documented within 30 days prior to consent.
4. HFH within 12 months prior to consent and/or elevated NT-proBNP (or BNP) within 30 days prior to consent defined as:
 - a. Subjects with LVEF ≤ 40%: NT-proBNP ≥ 1000 pg/mL (or BNP ≥ 250 pg/mL).
 - b. Subjects with LVEF > 40%: NT-proBNP ≥ 700 pg/mL (or BNP ≥ 175 pg/mL).
 - c. Thresholds for NT-proBNP and BNP (for both LVEF ≤ 40% and LVEF > 40%) will be corrected for BMI using a 4% reduction per BMI unit over 25 kg/m²
5. ≥ 18 years of age
6. Chest circumference of < 65 inches, if BMI is > 35 kg/m²
7. Written informed consent obtained from subject

8. Willing and able to upload PA pressure information and comply with the follow-up requirements

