5.4.1 Screening Procedures

The following information will be evaluated from medical records and documented, to ensure each subject meets entry criteria prior to consent. Subjects are required to have either a HFH within the previous 12 months or a documented elevated NT-proBNP (or BNP) within the previous 30 days (outside of clinical trial procedures per standard-of-care). Documentation of a prior HFH and/or elevated NT-proBNP (or BNP) is required for verification of inclusion and exclusion criteria. If necessary, screening procedures to address other entry criteria (such as EF and eGFR, if not previously documented) can be evaluated during the baseline visit following consent.

- Duration of HF from first diagnosis
- NYHA class evaluation within the previous 30 days
- All HFHs within the previous one year, as provided by the subject's cardiologist, internist, or referring physicians including gathering of source documentation of hospitalizations
- Laboratory analyses for qualifying NT-proBNP (or BNP) within the previous 30 days for inclusion verification (outside of clinical trial procedures)
- EF within six months prior to the consent date (can be from echo, nuclear testing, angiography, CT, MRI). If no documentation exists in the required timeframe, a limited echo to document EF only will be required during the baseline visit.

- Calculation of BMI using subject height and weight (see *Appendix H*) and calculation of chest circumference measurement if BMI > 35kg/m²
- Age
- Cardiovascular history including:
 - previous cardiac procedures and CRT device information
 - relevant co-morbidities
- HF medication review with documentation

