6.2.2.2.1 Analysis Methods

The hypothesis will be tested at the 2.5% significance level.

[REDACTED]

The null hypothesis will be rejected if the upper limit of the 1-sided, 97.5% CI for the HR of Post-Implant to Pre-Implant is less than 1.

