5.2.2.2.1 Hypothesis

The secondary endpoint will be evaluated using the following hypothesis:

H_0 : HR for annualized HFH at 12 months (Rate at 1 year post-implant to Rate at 1 year pre-implant) ≥ 1

H_1 : HR for annualized HFH at 12 months (Rate at 1 year post-implant to Rate at 1 year pre-implant) < 1

[REDACTED]

[REDACTED]

[REDACTED]

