5.2.2.2.2 Analysis Population

This secondary endpoint will be evaluated for the cohort of subjects enrolled into the Single Arm following successful implantation regardless of NT-proBNP (or BNP) and HFH history.

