5.2.2.2.5 Subgroup Analysis

The following 3 subgroups will be used for descriptive analyses (rates, hazard ratio and 2-sided 95% CI for the HR) of this secondary endpoint:

- a) elevated NT-proBNP only
- b) prior HFH only and
- c) both elevated BNP and HFH.

[REDACTED]

[REDACTED]

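### The Single Arm post- versus pre-implant HFH test is presented as demonstrating effectiveness, but entry depends in part on a prior-year HFH, so a ratio of 1 need not be the no-effect value

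*Protocol*

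**What the plan says.** Protocol section 6.2.2.2 introduces the test with "To demonstrate effectiveness of PA pressure-guided HF management with respect to the goal of reducing HFHs, the following hypothesis will be tested". The null hypothesis is a hazard ratio (post-implant year to pre-implant year) of at least 1. Section 6.2.2.2.1 sets a 2.5% level, with the null "rejected if the upper limit of the 1-sided, 97.5% CI for the HR of Post-Implant to Pre-Implant is less than 1". The matching SAP section, 5.2.2.2.1, is neutral: "The secondary endpoint will be evaluated using the following hypothesis". It still sits under the secondary effectiveness endpoints.

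The population is "subjects enrolled into the Single Arm following successful implantation regardless of NT-proBNP (or BNP) and HFH history" (SAP 5.2.2.2.2); protocol 4.3.2.2 agrees. Entry requires "HFH within 12 months prior to consent and/or elevated NT-proBNP (or BNP) within 30 days prior to consent defined as" the stated thresholds (protocol 4.4.1). The peptide-only group is defined as "subjects having elevated NT-proBNP (or BNP) but without having a HFH in the year prior" (protocol 6.2.1).

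SAP 5.2.2.2.5 adds output by entry group: "The following 3 subgroups will be used for descriptive analyses (rates, hazard ratio and 2-sided 95% CI for the HR) of this secondary endpoint". The groups are peptide only, prior HFH only, and both.

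Protocol 6.2.1.3 says that the Single Arm primary and secondary endpoints will support label claims. The rationale in protocol 6.3 is more modest than 6.2.2.2: it offers the comparison as an objective way to see whether hospitalizations went down after implant.

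**The concern.** A before-and-after test against 1 isolates a treatment effect only if, without treatment, the two years would have the same expected rate. Here the entry rule acts on the first year. Someone who enters only because of an HFH in the past year has a pre-period count that is high by selection, and regression to the mean lowers the following year's count with no help from the device. The Single Arm has no control group to measure that fall.

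At stake is the inference, not the arithmetic of the test. Under the stated purpose, a rejection would be read as proof that pressure-guided management works, and protocol 6.2.1.3 lets it support labelling. In the Randomized Arm, which has a control group, the same comparison is descriptive only (protocol 4.3.1.3, SAP 4.1.1.3).

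The subgroup output has a related problem. Peptide-only subjects have no HFH in the year prior by definition, apart from any between consent and implant. Their post/pre hazard ratio therefore has a denominator at or near zero.

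**Working it through.** **The plan's own figure.** An upper one-sided 97.5% limit below 1 corresponds to a 2.5% one-sided level, as stated. In simulated paired counts for 2600 subjects, with no device effect and no selection on the prior count, the mean ratio was 1.00 and rejection was 2.2% and 2.7% in two settings. The level holds when entry is unrelated to the prior count.

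**Inputs for the selected case.** From the documents: the entry rule, the pooled population and the null of 1. Assumed, because the visible text gives no rates or mix: HFH counts are gamma-Poisson with mean *m* = 0.3–1.0 per year and shape *k* = 0.5–2; rates are stable; there are no deaths and no device effect; and the entry and analysis windows coincide. Peptide-positive subjects are taken as unselected on HFH count. A share *s* enters as prior HFH only, drawn from the same rate distribution but with at least one HFH.

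**Formulas.**
- No HFH in a year: p0 = (k/(k+m))^k
- Expected rate given none: r0 = mk/(k+m)
- Expected rate given at least one: r1 = (m − p0·r0)/(1 − p0)
- Expected pre-period count given at least one: pre = m/(1 − p0)
- Pooled no-effect ratio: [(1−s)m + s·r1] / [(1−s)m + s·pre]

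**One case, m = 0.5, k = 1.** p0 = 0.667, r0 = 0.333, r1 = (0.5 − 0.222)/0.333 = 0.833, pre = 0.5/0.333 = 1.5.

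| Share s | Post | Pre | Ratio | Range over the grid |
|---|---|---|---|---|
| 5% | 0.475 + 0.042 = 0.517 | 0.475 + 0.075 = 0.550 | 0.94 | 0.88–0.98 |
| 20% | 0.400 + 0.167 = 0.567 | 0.400 + 0.300 = 0.700 | 0.81 | 0.67–0.93 |
| 50% | 0.250 + 0.417 = 0.667 | 0.250 + 0.750 = 1.000 | 0.67 | 0.47–0.86 |

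The low ends are at m = 0.3, k = 2 and the high ends at m = 1.0, k = 0.5. For example, at s = 50% the high end has r1 = 1.911 and pre = 2.366, giving (0.5 + 0.955)/(0.5 + 1.183) = 0.865.

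**What this does to rejection.** With 2600 subjects, m = 0.3–0.8, and a test on the log ratio of total counts with a paired robust standard error, simulated rejection with no device effect was about 17–77% at s = 5% and 95–100% at s = 20%. The plan's own estimation method is blacked out, so these figures describe a plausible test and not necessarily the planned one.

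**Other mixes.** Suppose recruitment fixes a share *w* with at least one prior HFH and the rest have none. The ratio is then [w·r1 + (1−w)·r0]/(w·pre). In the same case, w = 50% gives (0.417 + 0.167)/0.75 = 0.78, and w = 20% gives (0.167 + 0.267)/0.30 = 1.44. The ratio is exactly 1 at w = 1 − p0 = 0.33 (0.21–0.56 over the grid).

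**Rising rates.** In the case with ratio 0.81, a rise of 1/0.81 = 1.24, about 24% in a year, would bring the no-effect ratio back to 1.

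**Reading a result.** A pooled ratio of 0.81 is what the model gives for no effect at s = 20%. It is also what a true 19% reduction would give with no selection. The test alone cannot separate the two.

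**The case against.** The strongest reply is that entry is by HFH and/or peptide. Subjects with both features, and those with the peptide alone, qualify on the peptide whatever their HFH count, so together they are not selected on it. That is right. A reader might infer that everyone with a prior HFH is selected on it, and so apply the no-effect ratio for subjects with at least one prior HFH, 0.34–0.81 on this grid, to the test. That is a subgroup figure. In the pooled test only prior-HFH-only subjects enter because of the count, and the pooled ranges above are the relevant ones.

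Second, the direction is not settled. The protocol describes heart failure as progressive, so rates may rise; deaths are ignored; and the mix is not visible. Selection is also imperfect. Screening gathers "All HFHs within the previous one year" from site records (protocol 5.4.1), whereas endpoint HFHs are adjudicated (Appendix C) and counted back from implant. All of this stands. It rules out saying that the test must favour the device, but it does not make 1 the no-effect value.

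Third, the estimation method, sample size and multiplicity text are blacked out and may contain an adjustment. That cannot be excluded and is not criticised. The visible null, rejection rule and purpose are unaffected.

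Fourth, the SAP wording is already neutral, the rationale in protocol 6.3 claims only a decrease, and the entry groups are reported separately. These points narrow the defect mainly to the protocol's stated purpose. Group output shows the mix but does not remove selection within a group.

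**Conclusion.** The point holds in limited form. The test can show that the pooled HFH rate fell after implant; it cannot show that pressure guidance caused the fall. Under the stated assumptions the pooled no-effect ratio lies below 1, modestly at a 5% prior-HFH-only share and substantially at 20% or 50%. Under other mixes or rising rates it could be 1 or above, in which case a real benefit could be missed. The size is illustrative throughout.

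Two stronger readings are not supported. One is that a false positive is assured: that needs rates and a mix that the documents do not give. The other is that the endpoint must be demoted to descriptive: the comparison answers the question posed in protocol 6.3, and demotion would be a design preference. Nor is Single Arm success at risk, since SAP 5.7 rests it on the primary endpoint. The consequence is confined to the effectiveness wording, the label use and one subgroup statistic. It should be fixed.

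**What to change.** Keep the test as a secondary endpoint.

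1. In protocol 6.2.2.2, replace the opening clause that states the effectiveness purpose with: *To evaluate whether the HFH rate decreased after implantation compared with the year before*.
2. Add to protocol 6.2.2.2 and SAP 5.2.2.2: *Because entry depends in part on prior-year HFH, the post/pre ratio may differ from 1 without any device effect; results will be shown by entry group and no effectiveness or label claim will rest on the pooled ratio alone.*
3. In SAP 5.2.2.2.5, for the elevated NT-proBNP (or BNP) only group, replace the hazard ratio and its interval with the post-implant HFH rate and 95% CI.

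The cost is wording. The endpoint keeps its place, so the other sections that list it and the blacked-out multiplicity text need not change on this account. The sponsor gives up a causal before-and-after claim that this comparison cannot support.

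Separately, two inconsistencies should be reconciled. Prior HFHs are counted back from consent (protocol 4.4.1), from baseline (5.10.4, 8.2.1) or from implant (6.2.2.2). The consent-to-implant window is 60 days in protocol 4.1.3 and 5.4.4 but 30 days in SAP 3.1.2.
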